1.0 Project Summary/Abstract

Cardiovascular disease is the leading cause of death worldwide, with ischemic heart disease (IHD) the leading cause of cardiovascular mortality. Persons with IHD suffering from psychological distress, including hopelessness, are more likely to die from IHD. Following a stressful event, the vagus nerve enables activation of either a sympathetic (fight/flight) or parasympathetic (rest/digest) response. Heart rate variability (HRV), the beat-to-beat variability between normal successive heart beats, is a biomarker of both adaptive and maladaptive reactions to stress. Decreased HRV predicts greater risk for morbidity and mortality and is associated with poor mental health outcomes in persons with IHD. As stated by polyvagal theory, HRV may be influenced by social support. Decreased perceived social support (PSS), a social determinant of cardiovascular risk, is predictive of increased morbidity and mortality in persons with IHD. Decreased PSS has been associated with hopelessness in patients with cancer, but this relationship has not been studied in IHD beyond the applicant's small pilot study of patients with hopelessness. Hopelessness, a negative outlook and sense of helplessness about the future, is present in 27-52% of patients with IHD. This is of grave concern, because hopelessness is associated with a 3.4 times increased risk of mortality and nonfatal myocardial infarction in patients with IHD, independent of depression. This research focuses on understanding the biological (HRV) and social (PSS) aspects of hopelessness, with the long-term goal of developing and testing novel interventions to reduce the adverse effects of hopelessness and improve health outcomes in patients with IHD. Participants for this cross-sectional study will be recruited while hospitalized for an IHD event. Participants will include patients who report moderate to severe hopelessness from [name] NIH-funded study (R01NR017649, $n = 225$); additional patients with minimal to no hopelessness will be recruited and enrolled by the applicant ($n = 45$). Data collection will take place remotely two weeks after hospital discharge. Specific aims include: Aim 1) Evaluate the relationship between HRV and hopelessness in patients with IHD; Aim 2) Determine the relationship between PSS and hopelessness in patients with IHD; and Aim 3) Explore the possible mediating effect of HRV on the relationship between PSS and hopelessness in patients with IHD. The outcomes of this proposed study and the training plan will prepare the PhD student to launch a program of research focused on the biological and social dynamics of symptoms experienced in patients with IHD, with a long-term goal of promoting personalized health treatments for persons with IHD.

2.0 Objectives/Aims

Specific Aims are to:

Aim 1: Evaluate the relationship between HRV and hopelessness in patients with IHD.

Hypothesis: Higher levels of HF HRV will be associated with lower levels of hopelessness.

Aim 2: Determine the relationship between PSS and hopelessness.

Hypothesis: Higher levels of PSS will be associated with lower levels of hopelessness.

Aim 3: Explore the possible mediating effect of HRV on the relationship between PSS and hopelessness.

Hypothesis: HF HRV will mediate the relationship between PSS and hopelessness.

* As an extension of [name] NIH-funded study (<https://clinicaltrials.gov/ct2/show/NCT03907891>), data collected from patients with IHD who report moderate to severe hopelessness will be analyzed to examine the aims. The PI of this study (Hope Beats) will also collect and analyze data from patients with minimal to no hopelessness. The data collected from patients reporting minimal to no hopelessness are presented in this clinical trial registration.

3.0 Eligibility

3.1 Inclusion Criteria

- Eligibility criteria for hopelessness screening include: Adults \geq 18 years old; diagnosed with myocardial infarction, unstable angina, or who undergoing percutaneous coronary intervention or coronary artery bypass graft surgery; speak and read English; and can complete the screening instrument.

3.2 Exclusion Criteria

- The following exclusion criteria are in place because they alter heart rate variability: having a pacemaker or implanted cardioverter-defibrillator, chronic arrhythmia, history or current valvular disease, history of organ transplant, current use of immunosuppressive medications, or diabetic autonomic insufficiency. Although research conducted in 2016 identified HRV diminishing with age when controlling for disease and medication use, more recent research has identified no relationship between HRV and age. A study of healthy individuals, controlling for other health conditions, did not find any relationship between resting HRV and age in adults older than 40. Another study of healthy participants identified no significant difference in resting HRV between persons in the age group 40-49 compared to 50-59. Because the median age for a male with IHD is 65 years and for females is 70 years, the age range of 40-80 years was chosen to be representative of the IHD population and to mitigate the confounding effect of age on HRV.

3.3 Excluded or Vulnerable Populations

- Only English-speaking patients are eligible to enroll in the study, because not all instruments are readily available in languages other than English.

4.0 Subject Enrollment

The PI will screen potentially eligible patients over the phone or in person. Screening will include asking patients if they meet any of the exclusion criteria described above. Patients who are eligible for enrollment after screening will be asked by the PI to participate in the proposed research. The PI will read through a script to describe the study. If a patient agrees to enrollment in the study, written consent will be obtained. If the participant is enrolled after hospital discharge, they will be sent a link via email or text message, which will take them to the REDCap e-consent page, where they will provide an electronic signature. After the electronic signature is accepted and confirmed, a copy of the signed e-consent will be sent to the patient by email and/or postal mail and a copy will be saved in the REDCap database.

5.0 Study Design and Procedures

Human Subjects Involvement, Characteristics, and Design

The proposed study uses a cross-sectional design. Patients enrolled in [name] study (until March 3/6/2023) with moderate to severe hopelessness and the additional 45 patients recruited who screen to have minimal to no hopelessness by the PhD student will be included in the analysis of Aim 2. Aims 1 and 3 will include patients from [name] study who meet the stated inclusion and exclusion criteria for the proposed study, in addition to the 45 patients who report minimal to no hopelessness. Both groups of patients (moderate to severe hopelessness and minimal to no hopelessness) will complete the same hopelessness screening in the hospital and the Week 2 data collection measures.

Data Collection Procedures. Study participants will receive a study package by USPS mail two weeks after hospital discharge plus or minus two days and will also receive an instructional phone visit at Week 2. Study package materials will include a Polar H7 heart rate monitor, ActiGraph wGT3X-BT (to link to the Polar monitor for HRV data collection), written instructions for HRV measurement, hard copies of questionnaires (to read along with during the data collection phone call), instructions to return the monitors, and a prepaid return envelope. Participants will also be sent a secure link via text or email to an instructional video depicting verbal and visual demonstration of proper placement for the Polar H7 heart rate monitor and ActiGraph wGT3X-BT. The PI will call the participant once a mail delivery notice has been received. During the call, the PI will confirm proper placement of the two monitors used to measure HRV and answer any questions. All data collection will occur at Week 2. Study measures and their characteristics can be found in Table 1.

Heart Rate Variability Procedures. At Week 2, participants will be instructed to place the Polar H7 heart rate monitor around the center of their chest, in contact with the skin, and the ActiGraph wGT3X-BT around their waist, according to directions outlined in the written instructions provided and as demonstrated in the instructional video and practiced with the applicant over the phone. Participants will be informed that the monitors are used to gather data about their body at rest. The Polar H7 heart rate monitor connects to the ActiGraph with Bluetooth® wireless technology so that the interval between normal heart beats (RR data) can be transferred to csv files for analysis. The HRV protocol will take place during a 10-minute time period on two consecutive days, to ensure at least one 10-minute time frame of usable data. Participants will be instructed to place the monitors first thing in the morning after they wake up and empty their bladder. Once the monitors are placed, participants will be instructed to lay supine quietly for 10 minutes and avoid moving or using any devices or watching tv. The standardized HRV protocol improves reliability of the HRV measurement because control of extraneous variables is maintained. Respirations will not be controlled because this can artificially increase HF HRV. The gold standard amount of time for a short-term HRV recording is 5 minutes. The 5 minutes of the recording with the least amount of artifact will be used for analysis. After 10 minutes of recording are completed, the heart rate monitor and ActiGraph will be removed. After the participant completes the 10-minute HRV measurements on two consecutive days, they will be asked to return the monitors in a prepaid envelope that will be

picked up from their mailbox by USPS and returned to the PI, mitigating any exposure to COVID-19.

Phone Visit to Complete Questionnaires. After completion of the HRV measurement instructional phone visit, participants will receive their Week 2 data collection visit. Participants in the PI's study will receive their phone visit from the PI. The PI will follow a script for data collection. Data collection interviews will take on average 20 minutes. During the phone visit, the data collector/PhD student will first ask how HRV measurement went that morning and remind participants to complete the measurement the following morning. Participants will then be asked to complete the four questionnaires indicated at the Week 2 timepoint in Table 1 (demographic questionnaire, State-Trait Hopelessness Scale, ENRICH Social Support Inventory, and Patient Health Questionnaire-9). Demographic data are being collected to describe the sample and determine if these variables are confounders. Depressive symptoms are being measured as a potential covariate because of the known association between hopelessness and depression.¹⁶ Upon completion of data collection, participants will be compensated \$20 for their time and commitment to the study. This is the same amount that patients enrolled in [name] study receive after their Week 2 visit. All questionnaire and electronic medical record data will be logged directly into REDCap using a secure electronic tablet. Data from medical records will be collected within 2 weeks of the participant's hospital discharge.

Measures. Characteristics of study measures appear in Table 1.

Table 1. Study Measures, Concepts, Variables, & Psychometric Properties

Measure	Concept	Time-point	# Items	Range	Description	Reliability/Validity
Polar H7 Heart Rate Monitor	Heart rate variability	Week 2	NA	Varies by domain	
 Monitor is worn across patient's chest to provide heart rate data Monitor has Bluetooth capabilities with ActiGraph WGT3X-BT so RR data can be transferred to csv files for analysis 	Strong correlation with ECG for measuring short-term HRV ($r=0.99$)
Demographic Questionnaire	Demographics	Week 2	17	NA	
 Age, sex, race, smoking status, ability to participate in physical activity, history of depression, marital status, education level, insurance status, employment status 	NA
State-Trait Hopelessness Scale (STHS)	State and trait hopelessness	Week 2	23	1-4	
 4-point Likert-type scale: 1 = strongly disagree, 4 = strongly agree Differentiates state and trait hopelessness Adding the item scores and dividing by the number of items provides a total score for each subscale 	
 Reliability: state $\alpha = 0.87$, trait $\alpha = 0.87$ Concurrent and predictive validity with IHD patients
ENRICH Social Support Inventory (ESSI)	Perceived social support	Week 2	5	5-25	
 5-point Likert-type scale: 1 = none of the time, 5 = all of the time Items summed for score: higher scores indicate greater perceived social support 	Found valid and reliable in patients with IHD
Patient Health Questionnaire -9 (PHQ-9)	Depressive symptoms	Week 2	9	0-27	
 Measures depressive symptom severity Items scored on a Likert-type scale from 0 = not at all to 3 = nearly every day and summed for a total score Separate cognitive and somatic depressive symptoms dimensions have been validated in patients with IHD 	Internal reliability and criterion and construct validity previously established
Medical Records Abstraction Form	Clinical characteristics	Hospital	5	NA	
 Two purposes: 1) To confirm eligibility and 2) To collect diagnoses, cardiovascular procedures, and admission height and weight 	NA

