11.0 Regulatory Requirements

11.1 Informed Consent

The recruiting hospital is responsible for recruiting, consenting and screening eligible patients (i.e., those who are screened as hopeless) for [name] study. Interested patients will provide verbal consent for the hopelessness screening, including a HIPAA waiver. The screening consent includes permission for review of the patient's medical records to collect patient

characteristics and comorbidities. Those patients who do not qualify for [name] study will be referred to the PI for assessment of eligibility for the PI's study.

Patients who do not meet the hopelessness criteria for [name] study (they have minimal or no hopelessness) will be approached by the PI to discuss possible enrollment in the proposed study. The PI will screen patients over the phone or in person to ensure they do not meet any of the study exclusion criteria. If a patient is eligible and agrees to enrollment in the study, written consent will be obtained. The consent will explain the study, risks, benefits, voluntary nature of participation, and the patient's right to discontinue participation at any time without consequences. If the participant is enrolled after hospital discharge, they will be sent a link via email or text message, which will take them to the REDCap e-consent page, where they will provide an electronic signature. After the electronic signature is accepted and confirmed, a copy of the signed e-consent will be sent to the patient by email and/or postal mail and a copy will be saved in the REDCap database.

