All adverse events and unanticipated problems will be reported to the PI's advisor within 24 hours. If the advisor evaluates the adverse events and unanticipated problems to be moderate or serious, she will notify the PI and convene the SMC. All unanticipated problems or serious adverse events that may be related to the study protocol will be reported by the PI to the university IRB and hospital IRB within 48 hours of the committee meeting. The PI will immediately respond and closely monitor any reported adverse events and unanticipated problems. The PI will enter all adverse events and unanticipated problems into the study database. Regardless of whether an adverse event or unanticipated problem is related to the study protocol, the participant's primary care provider will be notified of an event if it affects the patient's clinical status.

APPENDICES

Appendix A	Screening, Recruitment, and Enrollment
A1	Eligibility Screening for Hopelessness
A2	Exclusion criteria for Enrollment in PI's Study
Appendix B	Data Collection Script
B1	Week 2 Data Collection Script
Appendix C	Participant Documents
C1	Written Instructions to Complete Heart Rate Variability Measurement
C2	Directions to Return Monitors after Heart Rate Variability Measurement
Appendix D	Data Collection Instruments
D1	State-Trait Hopelessness Scale
D2	ENRICH Social Support Instrument
D3	Demographic Instrument
D4	Patient Health Questionnaire

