7. Typically, I believe I can help improve things.	Strongly disagree	Disagree	Agree	Strongly agree
8. Typically, I feel giving up would be easier.	Strongly disagree	Disagree	Agree	Strongly agree
9. Typically, I believe I will accomplish what I set out to do.	Strongly disagree	Disagree	Agree	Strongly agree
10. Typically, I believe that things will improve.	Strongly disagree	Disagree	Agree	Strongly agree
11. Typically, I believe I cannot make a difference.	Strongly disagree	Disagree	Agree	Strongly agree
12. Typically, I doubt that anything is worthwhile.	Strongly disagree	Disagree	Agree	Strongly agree
13. Typically, I believe I am powerless to change my future.	Strongly disagree	Disagree	Agree	Strongly agree

D2: ENRICHED Social Support Instrument

5-item ENRICHD Social Support Instrument

1	Is there someone available to whom you can count on to listen to you when you need to talk?	none of the time	a little of the time	some of the time	most of the time	all of the time
2	Is there someone available to you to give you good advice about a problem?	none of the time	a little of the time	some of the time	most of the time	all of the time
3	Is there someone available to you who shows you love and affection?	none of the time	a little of the time	some of the time	most of the time	all of the time
4	Can you count on anyone to provide you with emotional support (talking over problems or helping you make a difficult decision)	none of the time	a little of the time	some of the time	most of the time	all of the time
5	Do you have as much contact as you would like with someone you feel close to, someone in whom you can trust and confide in?	none of the time	a little of the time	some of the time	most of the time	all of the time

D3: Demographic Instrument

Demographics

1. What is your age in years?

2. What is your sex?

- (1) Female
- (2) Male

3. Are you of Hispanic or Latino origin?

- (1) Yes
- (2) No

4. What is your race?

- (1) White
- (2) Black/African American
- (3) American Indian or Alaska Native
- (4) Native Hawaiian or other Pacific Islander Asian
- (5) Other _____

5. What is your marital status?

- (1) Married
- (2) Separated
- (3) Divorced
- (4) Widowed
- (5) Never been married

6. Have you ever been diagnosed or treated for depression?

- (1) Yes
- (2) No

7. What is the highest grade of school or year of college you completed?

- (1) Eighth grade or less
- (2) Some high school
- (3) High school graduate
- (4) Some college
- (5) College graduate (bachelors)

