- (6) Some post-graduate college work (masters, doctoral)
- (7) Graduate with masters- or doctoral-level degree

8. What is your current job status?

- (1) Employed full-time
- (2) Employed part-time
- (3) Retired
- (4) Disabled or unable to work
- (5) Student
- (6) Other (please list) _____

9. What type of health insurance do you have?

- (1) Medicare
- (2) Medicaid
- (3) Government VA
- (4) Employer provided
- (5) Privately purchased
- (6) No health insurance

D4: Patient Health Questionnaire

Patient Health Questionnaire (PHQ-9)

1. Little interest or pleasure in doing things	not at all	several days	more than half the days	nearly every day
2. Feeling down, depressed or hopeless	not at all	several days	more than half the days	nearly every day
3. Trouble falling or staying asleep, or sleeping too much	not at all	several days	more than half the days	nearly every day
4. Feeling tired or having little energy	not at all	several days	more than half the days	nearly every day
5. Poor appetite or overeating	not at all	several days	more than half the days	nearly every day
6. Feeling bad about yourself, or that you are a failure or have let yourself or your family down	not at all	several days	more than half the days	nearly every day
7. Trouble concentrating on things, such as reading the newspaper or watching television	not at all	several days	more than half the days	nearly every day
8. Moving or speaking so slowly that other people could have noticed? Or the opposite - being so fidgety or restless that you have been moving around a lot more than usual.	not at all	several days	more than half the days	nearly every day
9. Thoughts that you would be better off dead or of hurting yourself in some way	not at all	several days	more than half the days	nearly every day
10. If you checked off any problems, how difficult have these problems made it for you to do your work, take care of things at home, or get along with other people?	not difficult at all	somewhat difficult	very difficult	extremely difficult

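### Table 1 describes a 17-item demographic questionnaire covering smoking and physical-activity ability; the printed form (Appendix D3) has 9 items and neither variable

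*Combined protocol and SAP*

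**What the plan says.** Table 1 (Section 5.0) describes the demographic questionnaire as a Week 2 measure with 17 items and gives its content as "Age, sex, race, smoking status, ability to participate in physical activity, history of depression, marital status, education level, insurance status, employment status". The text just before the table states the purpose: "Demographic data are being collected to describe the sample and determine if these variables are confounders".

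The appendix list names the form, D3, as "Demographic Instrument". As printed, D3 starts with age and ends with "9. What type of health insurance do you have", and the PHQ-9 (D4) follows directly. One of its items, "3. Are you of Hispanic or Latino origin", covers a variable that Table 1 does not list.

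The Week 2 script (Appendix B1) tells the caller to ask what is on the form and adds no demographic questions of its own. The medical records abstraction form has a second role in Table 1: "To collect diagnoses, cardiovascular procedures, and admission height and weight". Section 8.0 adjusts the Aim 1 model for relevant demographic and other covariates, with age and sex as examples, and Aim 2 refers back to that set.

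**The concern.** The table and the form disagree on both length and content, and the form determines what a participant is asked. A caller who follows B1 and D3 as printed collects nothing on smoking or physical-activity ability, although the protocol names both among the variables it will examine as confounders.

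The study is cross-sectional. Its first two aims, HRV with hopelessness and perceived social support with hopelessness, rest on regression adjustment. A candidate confounder that was never recorded cannot be examined or adjusted for, and all data are collected once, at Week 2. The planned confounder check would then be incomplete, and a report that listed all ten variables as considered would be wrong.

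**Working it through.** No power or sample-size formula applies. The check is a count and an item-by-item match.

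**Can the stated 17 be reproduced?** No count that was tried gives it:

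- numbered items on D3: 9
- D3 items plus the two write-in fields (race, job status): 9 + 2 = 11
- variables named in Table 1: 10
- those variables plus Hispanic or Latino origin: 10 + 1 = 11
- D3 items plus the 5-item abstraction form: 9 + 5 = 14

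The shortfall of D3 against Table 1 is 17 − 9 = 8 items.

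**Match of variables**

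| Variable | Named in Table 1 | On D3 |
|---|---|---|
| Age | yes | item 1 |
| Sex | yes | item 2 |
| Hispanic or Latino origin | no | item 3 |
| Race | yes | item 4 |
| Marital status | yes | item 5 |
| History of depression | yes | item 6 |
| Education | yes | item 7 |
| Employment | yes | item 8 |
| Insurance | yes | item 9 |
| Smoking status | yes | absent |
| Physical-activity ability | yes | absent |

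Eight of the ten named variables are on D3, two are absent, and one D3 item is not named in Table 1.

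**Are the other Week 2 questionnaires also printed short?** No.

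- STHS: 10 state + 13 trait = 23 items, against 23 in Table 1. The last trait item, "13. Typically, I believe I am powerless to change my future", is there.
- ESSI: 5 items, against 5.
- PHQ-9: 9 scored items (9 × 3 = 27, the top of the stated range) plus an unscored difficulty question, against 9.

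D3 is the only one of the four that falls short.

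**Could the two variables come from elsewhere?** The abstraction form, as Table 1 describes it, lists neither. The form itself is not among the appendices, so it cannot be checked further. Section 11.1 is broader: "The screening consent includes permission for review of the patient's medical records to collect patient" characteristics and comorbidities. That could cover smoking but does not say so.

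**The case against.** The strongest reply is that this may be a printing matter and not a gap in the data. Two forgotten questions do not explain the difference: one item for each missing variable brings D3 to 9 + 2 = 11, still 6 short of 17, whereas a longer working form would explain it. The appendices are also not a full set of instruments. The suicidal-ideation and adverse-event questions that B1 calls for are not printed, nor is the abstraction form. One race option on D3 appears to run two categories together, so D3 may not be an exact copy of what was used.

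This stands in part. An abridged print cannot be excluded, so the loss of data is conditional. Against it, D3 is numbered 1 to 9 without a gap, D4 follows at once with no mark of omitted text, and the other three questionnaires are printed in full.

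A second reply is that Section 8.0 names neither variable as a model term. That is correct. But age and sex appear there only as examples, and Section 5.0 assigns the confounder purpose to the demographic data as a whole.

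A third is that data collection may be over. Section 2.0 says the data from the minimal-to-no-hopelessness group are presented in the registration, and parent-study enrolment counts only to 3/6/2023. If so, adding questions comes too late. Reconciling the documents and reporting what was measured would still be needed.

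**Conclusion.** The concern holds. Table 1 and D3 contradict each other: 17 items stated and 9 printed, with 8 of the 10 named variables on the form. That much is certain from the text.

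The consequence for the analysis depends on which form was used. If it was D3 as printed, 2 of 10 candidate confounders are unavailable from the questionnaire for Aims 1 and 2. If it was a fuller form, the data exist and only the documents need correcting. The documents do not say how many of the 8 missing items would concern smoking or activity ability.

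No size of bias is claimed, because the documents give no figure for it. No difference between the two hopelessness groups is claimed either: Section 5.0 says both complete the same Week 2 measures, and the parent study's form is not shown. The point should be corrected before analysis.

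**What to change.** 1. Establish which demographic form was used. If it was longer than D3, print it as D3. If D3 is the working form, add items on smoking status and physical-activity ability, worded to match the parent study's Week 2 form so that both groups have the same measures.
2. Make the item count and variable list in Table 1 agree with the form, including Hispanic or Latino origin.
3. For participants whose Week 2 call is done and lacked these items, take smoking status from the medical record where the consent allows. Flag it as record-sourced, and report how many participants lack smoking or activity-ability data.
4. If the parent study's form lacks either item, report that variable as not measured in that group and do not list it as checked for confounding.

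The cost is a few more phone questions (the number depends on the parent form), corrections to Table 1 and D3, and an amendment at the two institutions that gave IRB approval. There are limits. New items cannot recover Week 2 answers already taken, and record-sourced smoking status differs in source from self-report. The applicant recruits only 45 of the 225 + 45 = 270 planned participants; the other 225 come from the parent study, whose form this protocol may be unable to change.

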8.0 Data Analysis

Data Analysis for Each Aim. Confirmation of the internal reliability of scales will be assessed using Cronbach's alpha. The following analyses will be used for each aim.

Aim 1: Kubios HRV software will be used to generate the HRV data for time, frequency, and nonlinear domain analyses. Kubios uses a threshold-based artifact correction algorithm that compares RR beats against a local average interval. The lowest level threshold that accurately detects artifact without overcorrecting normal beats will be used for each recording. Recordings with >5% artifact will not be used in analysis because even a small number of corrected ectopic or missing beats can have a great influence on short-term HRV results. To prevent the issue of not having useable data for a participant, participants are instructed to obtain the measurement at two separate timepoints. The recording with the least artifact will be used. The primary analysis for Aim 1 involves regressing hopelessness levels on HRV, after controlling for relevant demographic (e.g., age, sex) and other covariates (e.g., time of day, deviation from protocol,

etc.), using a multiple regression framework. All covariates as well as hopelessness and HRV levels will be normalized using transformations as needed; to ensure model robustness to variable distributions we will also apply rank-based approaches and bootstrapping of standard errors. As part of a sensitivity analysis, we will fit these same models within the two subgroups: those with moderate to severe hopelessness versus minimal to no hopelessness. Additional subgroup analyses will be completed to evaluate potential differences between sexes and type of IHD event and will include adding interaction terms to the models between sex or type of IHD event and HRV.

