Current use of immunosuppressive medications		
Diagnosed with diabetic autonomic insufficiency		

If "no" to all the above criteria, patient is eligible to enroll in the PI's study

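### The plan excludes immunosuppressant users because such drugs alter HRV, but no described instrument records any other medication, so Aims 1 and 3 as planned do not adjust for other HRV-active drugs

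*Combined protocol and SAP*

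**What the plan says.** Section 3.2 gives the reason for its exclusions: "The following exclusion criteria are in place because they alter heart rate variability". One item on the list is a drug class, "current use of immunosuppressive medications". It reappears as a yes/no line in the Appendix A2 checklist, where it serves eligibility only.

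The data sources for the analysis are described in Section 5.0 and the appendices:

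- **Medical Records Abstraction Form (Table 1):** five items, time-point hospital. It confirms eligibility and is used "To collect diagnoses, cardiovascular procedures, and admission height and weight".
- **Demographic questionnaire (Table 1):** 17 items, described as "Age, sex, race, smoking status, ability to participate in physical activity, history of depression, marital status, education level, insurance status, employment status". Appendix D3 prints nine numbered items. The closest to a medication question is item 6, "Have you ever been diagnosed or treated for depression", which is a lifetime question.
- **PHQ-9:** symptoms, not treatment.
- **Week 2 script (Appendix B1):** no question about drugs.

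In Section 8.0 the Aim 1 model regresses hopelessness on HRV, "controlling for relevant demographic (e.g., age, sex) and other covariates". Time of day and protocol deviation are given as examples, and the list is left open. The Aim 3 text names no covariates.

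**The concern.** This is an observational, cross-sectional study, so nothing balances background medication across levels of hopelessness. Every participant has had a myocardial infarction, unstable angina, PCI or CABG, and continues usual care. HRV is recorded about two weeks after discharge, so background medication is a live exposure at the time of measurement.

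The plan accepts that a drug can distort HRV and acts on that for one class. If another drug shifts HF HRV and its use also differs with hopelessness, it contributes to the Aim 1 coefficient. It also contributes to the HRV-to-hopelessness path in Aim 3 and, if use differs with social support, to the support-to-HRV path. An association of the hypothesised sign could then appear without a vagal link, or a real one could be masked. Aim 2 does not use HRV and is not affected by this route.

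An open covariate list does not help if the variable is not collected.

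**Working it through.** **Step 1. Is medication captured anywhere?** Tables 1, A1, A2, B1, D1 to D4, the consent scope in Section 11.1 and the Aim 1 and Aim 3 text were read for a medication field. The only one is the immunosuppressant line in A2. Three sources cannot be checked in full:

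- the abstraction form is not reproduced;
- D3 shows 9 of the 17 items stated in Table 1, so 17 − 9 = 8 are unseen;
- the parent-study forms are not in the document.

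Table 1's descriptions of the first two do not mention medication.

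**Step 2. Which sample size applies?** The pooled total is 225 + 45 = 270. Section 5.0 limits Aims 1 and 3 to parent-study patients who meet this study's criteria, plus the 45. That number is not stated, so 270 is an upper bound. A value of 150 is assumed for comparison.

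**Step 3. How large could the effect be?** The plan states no power calculation, alpha, drug prevalence or drug effect, so there is no figure to reproduce and every input here is an assumption. Suppose HRV and hopelessness are linked only through one unrecorded drug. Let p be the proportion using it, and d1 and d2 the user-versus-non-user differences in log HF HRV and in hopelessness, in within-group SDs. The size of the induced correlation is

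r = d1·d2·p(1−p) / √[(1 + d1²·p(1−p))(1 + d2²·p(1−p))].

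With p = 0.20 or 0.80, p(1−p) = 0.16. For d1 = d2 = 0.8: r = 0.64 × 0.16 / (1 + 0.64 × 0.16) = 0.1024 / 1.1024 = 0.093.

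The rejection rate of a two-sided 5% test follows from Fisher's z, with δ = atanh(r)·√(n−3) and rate = 1 − Φ(1.96 − δ) + Φ(−1.96 − δ). For r = 0.093:

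- n=270: δ = 0.0932 × √267 = 1.52, rate 33.1%.
- n=150: δ = 0.0932 × √147 = 1.13, rate 20.4%.

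| d1 / d2 | induced r | rate, n=270 | rate, n=150 |
|---|---|---|---|
| 0.3 / 0.3 | 0.014 | 5.6% | 5.3% |
| 0.5 / 0.5 | 0.038 | 9.6% | 7.5% |
| 0.8 / 0.5 | 0.060 | 16.5% | 11.2% |
| 0.8 / 0.8 | 0.093 | 33.1% | 20.4% |

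**Step 4. Cross-check on the correlation scale.** If the drug correlates 0.3 with HRV and 0.3 with hopelessness, the induced correlation is 0.3 × 0.3 = 0.09. The rate is 31% at n=270 and 19% at n=150, in line with the last row. Correlations of 0.1 and 0.1 give r = 0.01 and rates of about 5% at either size.

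The sign of r depends on whether the drug raises or lowers HF HRV and on whether it is more or less common in hopeless patients. The table gives the size only.

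**The case against.** The strongest reply is that absence of a described field is not proof that no field exists. The abstraction form is unseen. D3 is visibly incomplete, since smoking status is in Table 1 but not in D3. Table 1's list is not exhaustive either, since D3 asks about Hispanic origin and Table 1 does not mention it. The parent study supplies up to 225 of the 270 patients and may hold medication data. This stands as a limit on the claim. It does not remove the claim, because nothing shows that the same data exist for the 45 PI-enrolled patients, and no analysis text uses them.

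A reader might infer that adjustment is impossible. The documents do not support that: record review is already planned, it must confirm eligibility, and the covariate list is open. The supported statement is that adjustment is not planned.

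A reader might also infer that the hypothesised negative association is likely to be an artefact. That does not follow. Beta-blockers and antidepressants appear nowhere in the documents. Their effect on HRV is general pharmacology, taken here as an assumption, and a drug that raises HF HRV and is commoner in hopeless patients would work against the hypothesis.

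The phrase "HRV diminishing with age when controlling for disease and medication use" in Section 3.2 should not be pressed far. It describes one cited study of age, which the protocol sets against later findings. The immunosuppressant exclusion is the firm evidence that the plan regards a drug as altering HRV.

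PHQ-9, depression history and IHD event type are partial proxies. They do not measure current drug use, but they may absorb some of the bias. Finally, antidepressant use may follow from low mood, so putting it in the primary model risks adjusting for a consequence of the outcome. That objection stands and shapes the fix.

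**Conclusion.** The point holds in a limited form. The plan acts on one HRV-altering drug class, and no described instrument names another medication. As written, Aims 1 and 3 do not adjust for other HRV-active drugs, at least for the 45 PI-enrolled patients. The conclusion rests on Table 1's descriptions where the forms are not shown.

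Under the assumptions above, the false-positive rate lies between about 6%, close to nominal, and 33% at n=270; the top value is about 20% at n=150. The high end needs a drug with 0.8 SD differences on both variables. A drug used by nearer half the sample would do more, because p(1−p) rises from 0.16 towards 0.25. The direction is not known. Without medication data the study cannot tell a negligible bias from a material one, which is reason enough to make a cheap change.

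**What to change.** Add yes/no fields for beta-blocker, other rate-slowing or antiarrhythmic drug, and antidepressant or other anticholinergic drug. Ask them at the Week 2 call and take them from the discharge medication list during the record review already planned. Obtain the same fields for parent-study patients in Aims 1 and 3 from that study's data or from the chart. First confirm that consent covers this, because the screening consent in Section 11.1 refers to characteristics and comorbidities and does not name medication. If any of the forms not shown already hold these fields, say so in the plan.

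In Section 8.0, name beta-blocker and other rate-slowing drug use as covariates in the Aim 1 model and in both Aim 3 paths. Add antidepressant use in a sensitivity model only. Report estimates with and without medication adjustment.

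The cost is about a minute of call time, a few model terms and a chart look-up for parent-study patients. For those patients the discharge list only approximates use at the Week 2 recording, and this should be stated as a limitation. Treatment and enrolment do not change.
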